1.1 **Objective: What is the overall purpose of this research study?** (Limit response to 1-2 sentences.)

To determine the effectiveness of the IOPI in the management of treatment induced dysphagia following chemoradiation for oral pharyngeal cancer.

1.2 **Specific Aims: List the goals of the proposed study (e.g., describe the relevant hypotheses**

or the specific problems or issues that will be addressed by the study).

To compare standard exercise therapy plus IOPI to standard exercise alone to determine if recovery is enhanced and to determine if rate of recovery is accelerated.

1.3 Background: Briefly describe previous findings or observations that provide the background leading to this proposal.

The IOPI device is one of the most commonly used measurement techniques available to measure tongue strength and endurance. Some research studies have indicated that it can be used to investigate influences of age, gender and medical condition on tongue strength and speech.

1.4 Significance: Why is it important that this research be conducted? What gaps in existing information or knowledge is this research intended to fill?

This is a pilot study designed to look at any enhancement the IOPI device might have, when paired with standard therapy for dysphagia following chemoradiation.

View: 2.01

Section 2 - Research and Design Methods

2.1 Does this research study involve the use or evaluation of a drug, biological, or nutritional (e.g., herbal or dietary) supplement?

* No

2.1.1 Does this research study involve an evaluation of the safety and/or effectiveness of one or more marketed nutritional (e.g., herbal or dietary) supplements for the diagnosis, prevention, mitigation or treatment of a specific disease or condition or symptoms characteristic of a specific disease or condition?

*

2.1.1.1 List each of the marketed nutritional supplements being evaluated in this research study. Specify for each supplement the corresponding IND number or attach FDA correspondence specifying that an IND is not required.

Marketed nutritional supplement

IND number

There are no items to display

Upload FDA correspondence specifying that an IND is not required, if applicable:

Name Modified Date Version

View: 2.02

Section 2 - Research Design and Methods

2.2 **Will this research use or evaluate the safety and/or effectiveness of one or more devices?**

* Yes

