Once enrolled through written informed consent, research participants will be assigned to either "standard therapy" or to "standard therapy with IOPI" treatment group by a clinical investigator. This assignment will be in an alternating fashion based on date of enrollment. IOPI treatment consists of 10 repetitions of the IOPI exercises, three times a day on three days per week for 8 weeks. It will take 30 minutes to train the subject on how to do the exercises and record them and that it takes 5-10 minutes to complete 30 repetitions of the exercise. Subjects will be completing a diary related to their exercise regimen.

Subjects will undergo a standard of care modified barium swallow study by clinical staff prior to the onset of therapy to obtain baseline measurements of airway protection and oropharyngeal kinematic function. They will also be asked to complete a Visual Analog Scale (VAS) to rate their dysphagia prior to initiation of therapy, therapy by marking an "X" on a 100mm line indicating their perception of the severity of their dysphagia (0 = least severe, 100 = most severe). They will also be asked to complete a dietary assessment tool/questionnaire consisting of 10 items (EAT-10). Tongue isometric pressure generation (strength) will be measured with the IOPI. This requires the subject to press a small plastic air-filled bulb between the tongue and hard palate, which transfers isometric pressure on the IOPI. The Functional Oral Intake Scale (FOIS) will be used by the clinician to rate current level of oral intake. Finally subjects will be weighed.

Approximately 8 weeks after the initiation of therapy ("standard" or "standard w/ IOPI") individuals will be asked to complete the VAS and the EAT-10, and the clinician will repeat the FOIS and weigh the subjects, once again at their 8-week standard of care clinical follow up visit. 8 weeks is the usual standard of care follow up visit. A modified barium swallow (MBS) test will also be performed as part of standard of care at about the 8 week time point (after therapy). Finally isometric pressure (tongue strength) will be measured at this point.

At 8 weeks, individuals who were assigned to the "standard therapy only" group, who still require swallowing therapy, will be asked if they would like to add the IOPI to their therapy

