3. medical history of pneumonia, feeding tubes
4. patient age and gender, date of completion or cancer treatment, type of chemotherapy and total radiation therapy dosage

Research information to be placed into medical records would include:

1. Outcomes of therapy (including IOPI results/tongue strength)
2. Changes of research outcome measures pertinent to patient clinical care.
3. Type of exercise regimen the participant used.

2.14.1 Will protected health information from a non-UPMC/Pitt HIPAA covered entity be obtained for research purposes or will research data be placed in the non-UPMC/Pitt medical record?

* No

If Yes, describe how the HIPAA requirements will be met:

I, [name] , certify that any member of my research team accessing, reviewing and/or recording information from medical records have completed the CITI Privacy & Information Security course or, if completed within the past year, the Internet-Based Studies in Education and Research (ISER) HIPAA for Researchers (Formerly RPF Module 6). The HIPAA certificates must be available for review if audited but do not need to be uploaded into this OSIRIS application.

* Yes

2.14.2 Are you requesting a waiver of the requirement to obtain written HIPAA authorization for the collection of the PHI?

* No

View: 2.15

Section 2 - Research Design and Methods**2.15 Does this research study involve the long-term storage (banking) of biological specimens?**

* No

2.15.1 Broadly describe the intended future use of the banked biological specimens:**2.15.2 Indicate the planned length of storage of the banked biological specimens:**

*

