2.15.3 Will biological specimens be stored **without identifiers or linkage codes?**

If you answer Yes, the samples will not be stored with any identifiers or linkage codes and it is highly unlikely to be linked back to the individual.

If you answer No, the samples will be stored with an identifier or linkage code and can be linked back to the individual.

*

View: 2.16

Section 2 - Research Design and Methods

2.16 **Will research participants be asked to provide information about their family members or acquaintances?**

* No

2.16.1 **Describe what information about the third party will be obtained from the participant:**

2.16.2 **If the information about the third party is of a private nature, can the identity of the third party be readily ascertained or associated with this information?**

*

Describe the **private information** that will be collected and recorded about the third party:

View: 2.17 - 2.18

Section 2 - Research Design and Methods

2.17 **What are the main outcome variables that will be evaluated in this study?**

1. Tongue pressure generation (strength).
2. Airway protection during swallowing (penetration-aspiration scale score of MBS data).
3. Pharyngeal residue after swallowing (pharyngeal retention scale rating of MBS data).
4. Swallowing impairment based on EAT-10, VAS, FOIS.
5. Swallow kinematic measures of MBS data on a swallow by swallow basis (videofluoroscopic image analysis with image processing software):
 - a. oral transit duration (duration of bolus transit through the oral cavity)
 - b. stage transition duration (measure of pharyngeal onset delay time)
 - c. duration of impaired oral containment (measure of bolus control in the oral cavity)
 - d. pharyngeal transit duration (duration of bolus transit from oral cavity to inferior pharynx)
 - e. pharyngeal response duration (duration of hyoid bone maximal movement during the swallow)
 - f. duration of upper esophageal sphincter opening
 - g. laryngeal closure duration (duration of airway closure)
 - h. we may analyze the magnitude of epiglottic inversion (rotation of the epiglottis during swallows which relates to laryngeal closure)

- i. we may analyze the magnitude of hyoid displacement (distance traveled by the hyoid bond during swallows)

2.18 Describe the statistical approaches that will be used to analyze the study data.

* Addressed below:

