We will perform t-tests to compare the dependent variable values from each measure (penetration-aspiration scores, pharyngeal retention scores, swallow kinematic measures, tongue pressure scores, EAT-10 scores, VAS scores, and patient weight. We may also perform ANOVAs and post hoc analyses to determine the main effect of treatment condition on the dependent variables, and to determine the presence of any interaction effects, and single subject analyses using the C statistic, to determine individual effect sizes for individual participants. Analyses will be designed to compare performance at the following time points:

1. between groups comparisons at time 1 (start of treatment) and at 2 (end of treatment) to evaluate differences between groups at the start and end of 8 weeks of therapy.
2. within groups comparisons between time 1 and 2 (standard therapy vs. standard therapy + IOPI) to evaluate the magnitude of differences from beginning to end of therapy.
3. within group comparison (standard treatment crossover only) at time 1 and time 3 (8 weeks after crossover of standard treatment subjects into standard therapy + IOPI) to evaluate the magnitude of differences from beginning of therapy to end of second phase of therapy (combined standard therapy, with crossover to standard + IOPI).

View: 2.19 - 2.19.6

Section 2 - Research Design and Methods

2.19 Will this research be conducted in (a) a foreign country and/or (b) at a site (e.g., Navajo Nation) where the cultural background of the subject population differs substantially from that of Pittsburgh and its surrounding communities?

* No

Note that copies of training records, licenses, certificates should be maintained in the study regulatory binder and are subject to audit by the Research Conduct and Compliance Office (RCCO).

In addition, individuals planning to conduct human subject research outside the United States must complete an optional module on the CITI training website: International Studies. [Click here](#) to access the instruction sheet for accessing optional CITI modules.

2.19.1 Address the following for each of the foreign/culturally different sites where this research will be conducted:

- Name of site
- Name of authorized individual (e.g., IRB Chair) from the local IRB or other human subject protections entity that is responsible for the review and approval of the project; upload approval letter with an English translation, if applicable

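### The 8-week between-arm comparison of tongue pressure uses neither age nor sex, although both are collected and the background names them as factors studied with the IOPI; the likely cost is small

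*Combined protocol and SAP*

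**What the plan says.** Section 1.3 (Background) reports that some studies have indicated of the IOPI that "it can be used to investigate influences of age, gender and medical condition on tongue strength and speech". It gives no direction or size for any such influence. Section 2.17 lists tongue strength first among several main outcomes and names none of them as primary. Section 2.6 has it measured with the IOPI before therapy and again at about 8 weeks.

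Entry is open to both sexes from age 18 with no upper limit (3.1, 3.2, 3.13). The medical-record items in 2.14 include "patient age and gender, date of completion or cancer treatment, type of chemotherapy and total radiation therapy dosage".

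On allocation, 2.3 calls the study randomized, but 2.6 has a clinical investigator make the assignment and states: "This assignment will be in an alternating fashion based on date of enrollment". No stratification is described.

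On analysis, 2.18 commits to this: "We will perform t-tests to compare the dependent variable values from each measure". Its first listed comparison is between groups at time 1 and at time 2. It adds an option: "We may also perform ANOVAs and post hoc analyses to determine the main effect of treatment condition on the dependent variables", and also "to determine the presence of any interaction effects", without identifying the interacting factors. No covariate is named for any analysis.

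**The concern.** The background picks out age and gender in connection with the outcome that heads the list in 2.17. The study admits a population in which both can vary widely and records both, but the analysis plan does not use them.

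Two things follow for the time 2 comparison of tongue pressure. First, whatever share of the variation age and sex explain stays in the error term, so the arm difference is estimated less precisely than the collected data allow. Second, if the arms differ in age or sex, that difference is carried into the raw 8-week contrast, where it could be taken for an IOPI effect or could mask one. The second matters more here than in a properly randomized trial. With alternation the next arm is known in advance, and the clinician who approaches the patient may also be an investigator (4.2). An imbalance therefore need not be a chance one.

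**Working it through.** **1. The plan's own figure.** Section 3.11 gives 50 + 50 subjects, which is the 100 in 3.10. Section 3.12 sets this by referral base and realistic recruitment. No alpha, power, effect size or SD is stated, so there is no power calculation to reproduce. Everything below assumes two-sided alpha 0.05, 50 per arm with no dropout, an 8-week SD of 1, and normal approximations.

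**2. Unadjusted time 2 comparison, as planned.**
- Standard error: sqrt(2/50) = 0.20 SD.
- Detectable difference at 80% power: (1.960 + 0.842) × 0.20 = 0.56 SD.
- Power at 0.5 SD: Φ(0.5/0.20 − 1.96) = Φ(0.54) = 70.5%.

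**3. Adding baseline tongue pressure.** The standard error is multiplied by sqrt(1 − ρ²), where ρ is the baseline-to-final correlation (assumed).

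| ρ | SE factor | SE reduction | Power at 0.5 SD |
|---|---|---|---|
| 0.3 | 0.954 | 4.6% | 74.6% |
| 0.5 | 0.866 | 13.4% | 82.3% |
| 0.7 | 0.714 | 28.6% | 93.8% |

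**4. Adding age and sex on top of baseline.**
- If they explain 5% of the variance left after baseline (assumed), the further factor is sqrt(1 − 0.05) = 0.975, a 2.5% cut in standard error.
- At ρ = 0.5 the standard error becomes 0.20 × 0.866 × 0.975 = 0.169, and power at 0.5 SD is Φ(2.96 − 1.96) = 84%, against 82.3% with baseline alone.
- If the 5% is taken as a share of total variance, the factor is sqrt((1 − ρ² − 0.05)/(1 − ρ²)). That gives 0.972, 0.966 and 0.950 for ρ = 0.3, 0.5 and 0.7, or cuts of 2.8%, 3.4% and 5.0%.
- In each row the baseline value gives the larger gain, though at ρ = 0.3 not by much.

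**5. Effect of a sex imbalance on the unadjusted difference.** Shift = sex difference (in SD) × difference in sex proportion between arms. Both inputs are assumed.

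| Sex difference | 10-point imbalance | 20-point imbalance |
|---|---|---|
| 0.2 SD | 0.02 SD | 0.04 SD |
| 0.5 SD | 0.05 SD | 0.10 SD |
| 0.8 SD | 0.08 SD | 0.16 SD |

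All of these lie below the 0.20 SD standard error from step 2. For age, the shift would be the slope per year times the difference in mean age; the documents give neither.

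**6. How often chance alone would produce such an imbalance.** Under simple random assignment the standard error of the difference in proportions is sqrt(2p(1 − p)/50). This is 0.087 for an assumed 75% male and 0.100 for 50% male. The probability of an imbalance of 10 points or more is then about 0.25 to 0.32, and of 20 points or more about 0.02 to 0.05. These apply to random assignment only. For predictable alternation no such distribution can be relied on.

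**The case against.** The strongest case against the point has five parts.

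- **The background sentence describes a use of the device, not a finding.** This stands. A reader might infer that the protocol treats age and sex as known prognostic factors, but 1.3 does not say so. The same sentence also names medical condition, and 2.14 also collects tumour site, stage, chemotherapy type and radiation dose. Age and sex are therefore a reasonable choice and not the only possible one.
- **Baseline would already carry much of any stable age or sex difference.** This is likely, and it is why the added gain is put at a few percent.
- **Chance imbalance is already covered by the t-test's standard error.** This is correct under random allocation, where leaving out covariates costs precision and does not bias the estimate. It does not fully protect this design, because alternation by a clinical investigator allows systematic imbalance. Age and sex terms would remove only the measured part of that imbalance and would not repair the allocation.
- **Section 2.18 offers other safeguards.** The time 1 comparison might reveal an imbalance in tongue strength, and within-group changes cancel stable characteristics. Neither adjusts the between-arm result. The ANOVAs are optional and name no age or sex term.
- **This is a pilot with feasibility-based enrolment.** An unadjusted comparison is then a legitimate choice, and no stated power target is missed. This lowers the urgency. The stated objective in 1.1 is nevertheless effectiveness, and between-group tests are planned.

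**Conclusion.** The point holds in a limited form and is minor to moderate. For tongue pressure, the committed 8-week comparison leaves out two collected variables that the background links to that outcome. It thereby gives up some precision and leaves any age or sex imbalance in the arm difference. The added gain over a baseline-adjusted model is probably small: about 2.5% in standard error if age and sex explain a further 5% of the remaining variance. The shift from a sex imbalance is 0.02 to 0.16 SD over the ranges tried. All these inputs are assumptions, because the documents give no variance, effect size or sex mix.

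Two stronger readings are not supported. A reader might compute that age and sex explaining 10% to 30% of the variance would be worth 11% to 43% more patients, from 1/(1 − R²). That R² has no source in the documents, and the comparison leaves out the baseline value that the trial measures. A reader might also extend the point to every continuous outcome. Section 1.3 speaks only of tongue strength and speech, so it gives no ground for the swallow-study measures, EAT-10, VAS or weight.

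**What to change.** In 2.18, replace the time 2 between-group t-test for tongue pressure with a linear model, fixed before any data are examined. Regress the 8-week value on arm, baseline tongue pressure, age (continuous) and sex, and report the adjusted arm difference with its 95% CI as the between-arm result. Baseline should be a required term, since most of the precision is likely to come from it.

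The cost is one sentence and no new data. With 100 complete subjects, a model with arm and baseline leaves 100 − 3 = 97 residual degrees of freedom; age and sex use two of these, leaving 95. Fixing the covariates in advance also prevents choosing them after the results are seen. The adjustment does not replace attention to the allocation method in 2.6, because it can correct only for what was measured.

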2.3.1 Does this research study involve a placebo-controlled arm?

* No

View: 2.04

Section 2 - Research Design and Methods

2.4 Will any research subjects be withdrawn from known effective therapy for the purpose of participating in this research study?

* No

2.4.1 Provide a justification for discontinuing subjects from known effective therapy for the

purpose of study participation.

2.4.2 **Describe the risks to subjects associated with discontinuing them from known effective therapy for the purpose of study participation.**

View: 2.05

Section 2 - Research Design and Methods

2.5 **Will screening procedures (i.e., procedures to determine research subject eligibility) be performed specifically for the purpose of this research study?**

* No

2.5.1 **List the screening procedures that will be performed for the purpose of this research study. Do NOT include the inclusion/exclusion criteria in this section as they will be addressed in section 3; questions 3.13 and 3.14.**

2.5.2 **What steps will be taken in the event that a clinically significant, unexpected disease or condition is identified during the conduct of the screening procedures?**

Addressed below:

Participants will be under the clinical care of a member of the Department of Otolaryngology. Any disease or condition identified during the course of this research will be addressed following standard clinical procedure.

View: 2.06

Section 2 - Research Design and Methods

2.6 **Provide a detailed description of all research activities (e.g., all drugs or devices; psychosocial interventions or measures) that will be performed for the purpose of this research study.**

This description of activities should be complete and of sufficient detail to permit an assessment of associated risks.

At a minimum the description should include:

- **all research activities**
- **personnel (by role) performing the procedures**
- **location of procedures**
- **duration of procedures**
- **timeline of study procedures**

Individuals seen by Department of Otolaryngology physicians/clinicians, having developed treatment associated dysphagia after completing non-operative treatment with chemoradiation or radiation therapy alone, for oral, oropharyngeal, hypopharyngeal or laryngeal cancer, will be approached for participation during the course of usual clinical care in the Dept. of ENT clinical offices designated in this protocol.

Once enrolled through written informed consent, research participants will be assigned to either "standard therapy" or to "standard therapy with IOPI" treatment group by a clinical investigator. This assignment will be in an alternating fashion based on date of enrollment. IOPI treatment consists of 10 repetitions of the IOPI exercises, three times a day on three days per week for 8 weeks. It will take 30 minutes to train the subject on how to do the exercises and record them and that it takes 5-10 minutes to complete 30 repetitions of the exercise. Subjects will be completing a diary related to their exercise regimen.

Subjects will undergo a standard of care modified barium swallow study by clinical staff prior to the onset of therapy to obtain baseline measurements of airway protection and oropharyngeal kinematic function. They will also be asked to complete a Visual Analog Scale (VAS) to rate their dysphagia prior to initiation of therapy, therapy by marking an "X" on a 100mm line indicating their perception of the severity of their dysphagia (0 = least severe, 100 = most severe). They will also be asked to complete a dietary assessment tool/questionnaire consisting of 10 items (EAT-10). Tongue isometric pressure generation (strength) will be measured with the IOPI. This requires the subject to press a small plastic air-filled bulb between the tongue and hard palate, which transfers isometric pressure on the IOPI. The Functional Oral Intake Scale (FOIS) will be used by the clinician to rate current level of oral intake. Finally subjects will be weighed.

Approximately 8 weeks after the initiation of therapy ("standard" or "standard w/ IOPI") individuals will be asked to complete the VAS and the EAT-10, and the clinician will repeat the FOIS and weigh the subjects, once again at their 8-week standard of care clinical follow up visit. 8 weeks is the usual standard of care follow up visit. A modified barium swallow (MBS) test will also be performed as part of standard of care at about the 8 week time point (after therapy). Finally isometric pressure (tongue strength) will be measured at this point.

At 8 weeks, individuals who were assigned to the "standard therapy only" group, who still require swallowing therapy, will be asked if they would like to add the IOPI to their therapy

program (crossover). If they agree, they will be trained to use the IOPI and use it together with their "standard therapy" program for an additional 8 weeks. Lingual strength with the IOPI, weight, FOIS, VAS and EAT-10 will be collected both before and after the initiation of this addition to their therapy. A standard of care MBS will again be performed after 8 weeks of therapy with IOPI in this group. Those who still require swallowing therapy and do not wish to add the IOPI to their standard of care therapy program will continue in their standard therapy program.

Individuals (in either group) who do not require additional swallowing therapy at the end of study participation will discontinue their standard of care therapy program altogether.

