- process for child assent and parental permission
 - continued participation if a child subject turns 18 during participation
- process for obtaining proxy consent and assent for decisionally impaired subjects
 - continued participation if subject regains capacity to consent

The potential research subject will be approached by their clinician who may also be an investigator on this research study. The clinician or investigator will provide information about participation, including the purpose of the study, the potential risks and benefits of study participation, and their rights as a research subject. The clinician or the investigator will go through the informed consent document with the potential research subject prior to enrollment. The investigator and/or clinician will answer any questions that the potential research subject may have about this research study. Consent will ultimately be obtained by the clinician or one of the investigators on this project as approved by the IRB.

4.13 Are you requesting an exception to either IRB policy related to the informed consent process?

- For studies involving a drug, device or surgical procedures, a *listed physician* investigator is required to obtain the written informed consent unless an exception to this policy has been approved by the IRB
- For all other studies, a *listed* investigator is required to obtain consent (Note: In order to request an exception to this policy, the study must be minimal risk)

* Yes

If Yes, provide a justification and describe the qualifications of the individual who will obtain consent:

We are requesting an exception to the IRB policy requiring a "listed physician investigator" to obtain written informed consent from participants.

The reason for this request is that additional clinicians in the Department of Otolaryngology will have the required knowledge to complete the informed consent process. Currently, there are 5 Speech Language Pathologists (currently not listed as co-investigators) that will be directly involved in the care of the participants. These individuals will be assisting with the swallowing testing as well as instructing the subjects in the proper therapy techniques and proper use of the IOPI device. With proper instruction on the details of the protocol, these additional 5 SLPs who are assisting directly with the care of these individuals will be adequately qualified to answer questions related to this research.

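### Nothing in 2.6 requires baselines to be taken or the standard exercise regimen recorded before the arm is known, or keeps standard therapy comparable between arms, so the week-8 contrast may not isolate IOPI.

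*Combined protocol and SAP*

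**What the plan says.** The aim in 1.2 is an add-on contrast: "To compare standard exercise therapy plus IOPI to standard exercise alone".

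On assignment, 2.6 says "Once enrolled through written informed consent, research participants will be assigned to either" of the two groups, and that patients go to their "treatment group by a clinical investigator. This assignment will be in an alternating fashion based on date of enrollment".

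The baseline assessments come next in 2.6. The swallow study is timed: "Subjects will undergo a standard of care modified barium swallow study by clinical staff prior to the onset of therapy". The VAS is also timed to before therapy starts. EAT-10, tongue pressure, FOIS and weight follow in the same paragraph without a timing phrase of their own. None of these measures is timed relative to assignment.

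The device exercise is specified: "IOPI treatment consists of 10 repetitions of the IOPI exercises, three times a day on three days per week for 8 weeks", with the note that "it takes 5-10 minutes to complete 30 repetitions of the exercise". Standard therapy has no stated content, frequency or amount.

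Section 4.13 describes speech-language pathologists who will be "assisting with the swallowing testing as well as instructing the subjects in the proper therapy techniques and proper use of the IOPI device". The design answer in 2.3 lists no masking.

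Two records of exercise are planned: a patient diary about the exercise regimen (2.6), and a medical-record entry for the "Type of exercise regimen the participant used" (2.14). The analysis section, 2.18, uses neither.

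**The concern.** An add-on comparison isolates the added component only if the background is comparable in both arms. Here clinicians who know the arm are free to vary the background. A patient already doing IOPI work could be given, or could do, less standard exercise; a patient without the device could be given more. The first would tend to hide a real IOPI effect. A difference in the other direction could create an apparent effect where there is none. A t-test at week 8 cannot separate either from the effect of IOPI.

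This mechanism acts after assignment, so a better allocation method alone would not remove it. Section 5.7 keeps non-compliant patients in the study, which makes a record of the exercise actually done more important.

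The baselines raise a second issue. VAS and EAT-10 are self-reports, tongue pressure depends on effort, and FOIS is a clinician's rating. If they are taken once the arm is known, expectation can move them. Section 2.18 compares the groups at the start of treatment and also examines change from start to end, so a shifted baseline affects both.

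**Working it through.** The plan gives no alpha, power, effect size or SD. Section 3.12 bases the 50 per arm on referral numbers, so there is no calculated figure to reproduce. The check has three parts.

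**1. Does any section close the gap?**

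| Safeguard needed | What the documents give |
|---|---|
| Baselines taken before the arm is known | Swallow study and VAS timed to before therapy; nothing timed to before assignment (2.6) |
| Standard regimen recorded before the arm is known | Not stated; when and by whom it is set is not stated either |
| Standard therapy comparable between arms | No such requirement |
| Treating clinicians unaware of the arm | No masking listed (2.3); the same clinicians teach techniques and device (4.13) |
| Arm not foreseeable | Alternation by enrolment date (2.6), so the next arm can be predicted |
| Delivered exercise recorded | Diary, without saying whether it covers standard exercises (2.6); regimen type but not amount (2.14) |
| Delivered exercise used or reported by arm | Not in 2.18 |

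**2. How large is the added IOPI exercise?** Inputs from 2.6: 10 repetitions, 3 times a day, 3 days a week, 8 weeks, and 5-10 minutes per 30 repetitions.

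- Repetitions per day: 10 × 3 = 30, which takes 5-10 minutes.
- Per week: 3 × 5 = 15 minutes to 3 × 10 = 30 minutes.
- Over 8 weeks: 8 × 15 = 120 minutes to 8 × 30 = 240 minutes, or 2-4 hours.
- Total repetitions: 10 × 3 × 3 × 8 = 720.

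The single 30-minute training session is not counted. A between-arm difference of 15-30 minutes a week in standard exercise would equal the whole added exercise time. No assumption about the length of standard therapy is needed for this.

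**3. What could a background difference do to the test?** This part is illustrative. Assume two-sided alpha 0.05, 50 analysed per arm, equal SDs, no IOPI effect, and a shift of d SD in the week-8 mean caused only by unequal background therapy. The rejection rate comes from the noncentral t distribution with 98 degrees of freedom and noncentrality d / √(2/50).

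| d (SD, assumed) | Rejection rate (nominal 5%) |
|---|---|
| 0.1 | 7.9% |
| 0.2 | 16.8% |
| 0.3 | 31.8% |
| 0.4 | 50.8% |
| 0.5 | 69.7% |

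For scale, on the normal approximation 50 per arm has 80% power at (1.96 + 0.84) × √(2/50) ≈ 0.56 SD. The documents do not say which d, if any, would arise, and minutes of exercise cannot be converted into d from them.

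**The case against.** The strongest reply is that this is a self-described pilot adding a device to usual care, where leaving background therapy to clinicians is a recognised pragmatic choice. Section 4.11.2 tells patients that taking part does not alter their care. The crossover text in 2.6 has patients use IOPI together with their standard programme, so the intent is addition and not substitution. A diary is planned, and 2.6 does not restrict it to the IOPI arm.

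Much of this is fair, and it shows intent. But 4.11.2 concerns taking part or not, rather than one arm against the other. The crossover sentence applies only to the second 8 weeks for standard-arm patients. The diary might reveal an imbalance if it covers standard exercises, but it would not prevent one and no analysis of it is planned. Pilot status does not settle the matter, because 1.1 states the purpose as determining effectiveness. A pragmatic background is defensible if what was delivered is recorded and shown by arm.

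A second reply also stands: because assignment alternates, reordering the steps does not hide the coming arm from a clinician who knows the last one. The fix has to deal with that.

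A reader might go further and infer that the arm is assigned before the standard regimen is set. The order of consent, assignment, baseline and therapy makes that plausible, but the documents never say when or by whom the regimen is set. A reader might also take every baseline measure to be timed expressly to before therapy; that wording attaches only to the swallow study and the VAS.

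**Conclusion.** The point holds as a risk of bias. Nothing in the plan requires the baselines to be taken, or the standard regimen recorded, before the arm is known, or holds standard therapy comparable between arms. With unmasked clinicians teaching both components and no use of delivered exercise in 2.18, the week-8 contrast can mix the IOPI effect with a background difference in either direction.

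The documents fix the scale at 15-30 minutes a week, 2-4 hours in all, as the added exercise that a background difference would have to match. This compares exercise time only and does not assume that a minute of one exercise is worth a minute of another. The rejection rates above rest on assumed values of d and alpha.

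The documents do not support a claim that background therapy did differ, or that any baseline was in fact influenced. The change is worth making because it is cheap and because nothing done at analysis can recover standard exercise that was never recorded.

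**What to change.** In 2.6, set the order as: consent; all baseline measures; the clinician's usual standard regimen recorded on a short form; then assignment.

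Replace alternation by enrolment date with a concealed random sequence. If alternation is kept, the reordering still keeps patients unaware of their arm for VAS, EAT-10 and tongue pressure, but it does not shield the clinicians who rate FOIS and record the regimen.

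State that the existing diary records standard exercises in both arms. Log later changes to the standard regimen with date and reason. In 2.18, report completed standard exercise by arm beside the week-8 comparison. The content of standard therapy, and any clinical change to it, stay with the clinician.

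The cost is a few sentences in 2.6 and 2.18, one short form, one more diary column, and preparation of the concealed sequence. Assignment moves to the end of the baseline assessment. Since 2.6 already places the swallow study before therapy, this needs no extra visit.
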